5.2 Microbiological Methods

5.2.1 Microbial Sample Collection / Cup Scrub Technique

Quantitative cultures (treatment day baselines and post treatment samples) will be obtained by a modification of the cylinder sampling technique of Williamson-Kligman cup scrub technique following ASTM E1874-14 "Standard Test Method for Recovery of Microorganisms from Skin using the Cup Scrub Technique". To collect the samples, a sterile scrub cup (2.20 cm I.D.) will be placed on the site and held firmly to the skin. 3.0 ml of SSF++ will be pipetted into the cup and the skin will be scrubbed in a circular motion with moderate pressure for 1 minute using a sterile rubber policeman. Using a sterile transfer pipette, the SSF++ will be removed and placed in a sterile test tube. An additional 3.0 ml of fresh SSF++ will be pipetted into the cup and the scrub procedure will be repeated. This solution will be pooled with the first solution collected.

5.2.2 Bacterial Enumeration Methods

Following sample collection, vortex the sample for 15 seconds and 10-fold serial dilutions will be prepared using PBW. One ml aliquots of appropriate dilutions will be pour-plated in TSA+N. Samples must be plated within 30 minutes of collection.

Serial dilutions of collected treatment day samples as follows:

for groin sites:

- Baseline: 3 serial dilutions (10^{-3} , 10^{-4} and 10^{-5})
- 30 seconds: 4 serial dilutions (10^0 , 10^{-1} , 10^{-2} and 10^{-3})
- 10 minutes: 4 serial dilutions (10⁰, 10⁻¹, 10⁻² and 10⁻³)

After 72 \pm 4 hours of aerobic incubation at 30 \pm 2°C, colonies will be manually counted and viable cells in the original sample will be calculated according to SOPs. After incubation, plates may be refrigerated up to 48 hours prior to counting.

Bacterial colonies enumerated manually within the countable range 25-250 from each dilution will be recorded on the appropriate CRFs for each subject. The average number of microorganisms recovered (CFU/cm²) from the skin during treatment day will be calculated using the formula to convert the volume of sample collected into log₁₀CFU/cm² of skin:

$$R = log_{10} \left[\frac{F\left(\frac{\sum_{i=1}^{3} c_i}{n}\right) D}{A} \right]$$

Where:

R= the average colony-forming unit count in \log_{10} scale per cm² of sampling surface F= total number of ml of stripping fluid added to the sampling cylinder; in this study, F=6 ml $\frac{\sum_{i=1}^3 c_i}{n}=$ average of the triplicate colony counts used for each sample collected D= dilution factor of the plate counts

A = inside area of the cylinder in cm²; in this study, $A = 3.80 \text{ cm}^2$ for the 2.2-cm diameter cylinder.

6 Assessment of Efficacy

6.1 Efficacy Parameters

The measure of antimicrobial efficacy will be the log_{10} CFU/cm² of skin flora at the groin site 30 seconds and 10 minutes following study products application relative to the Treatment Day baseline log_{10} counts.

6.2 Assessment Methods

Efficacy will be assessed by sampling the skin using the cup scrub method and analysis methods described in Section 5.2.

7 Risk / Benefit Assessment

7.1 Potential Risks

Subjects participating in this study could experience side effects to the skin such as:

- Redness
- Swelling
- Burning, stinging and itching
- Cracking
- Peeling
- Small blisters or sores (in uncommon cases)
- Rash or other allergic reaction including in rare cases anaphylaxis
- Irritation
- Pain
- Localized rash or inflammation (dermatitis)
- Impetiginized eczema (infected eczema or infected dry skin and recurring skin rashes)
- Application site hypopigmentation (lightening of skin) or hyperpigmentation (darkening of skin).

Subjects may also experience folliculitis from clipping.

There may be risks from participating in this study that are unknown.

7.2 Potential Benefits

There are no direct benefits to the subject for participation in this study.

8 Assessment of Safety

8.1 Safety Parameters

The principal measures of safety will be skin irritation scores and the incidence of adverse events reported during the study.

Adverse events will be captured from the time the subject have signed the Informed consent form to the time of subject discharge from the study. Adverse events will be categorized in relationship to the product that was applied to the specific skin site. All local and systemic adverse events observed or reported to the investigator will be evaluated.

The severity, duration, causal relationship to the study product and study procedure, action taken (study related and subject related), study impact, outcome of the event; will be described for all adverse events.

8.2 Assessment Methods for Skin Irritation

All randomized subjects will be considered evaluable for safety. Skin irritation scores based on the scale from Appendix 17.6 will be reported for any subject who is scored with a 1 or more at any observation (baseline treatment day, clipping/re-clipping and prior/post-application to 30 seconds and 10 minutes sampling procedures), in any category for any site.

Adverse events (including post treatment skin irritation scores of 3), will also be summarized. Summary tables will present incidence rates of adverse events by treatment group for all subjects who enter the treatment period. Listings of adverse events will be provided.

A corresponding rating score for each individual skin condition, for each site will be recorded in the subject's CRF. (See Appendix 17.6, which includes the following four independent evaluation categories: Erythema, Edema, Rash, and Dryness).

If an irritation score of 1 or greater for any individual skin condition prior to the baseline sample collection (at treatment day phase) is assigned, the subject will be excluded from the study (no study treatment will be applied).

If an irritation score of 3 for any individual skin condition at any observation period is assigned, the subject will be discontinued from the study and an adverse event will be recorded. See Section 8.3 (Adverse Events).

8.3 Adverse Events

The PI is responsible for identifying adverse events that occur to each subject throughout the study and follow-up period. An adverse event can occur at any time during the conduct of the study, in any phase of the study or after the study is completed. An adverse event can be identified by the PI or sub-investigators or reported by the subject.

Definitions:

Adverse Event/Experience

An Adverse Event/Experience is any unexpected or undesirable experience occurring to a subject during a study, which may or may not be related to the test product.

All adverse events, regardless of severity or the causal/effect relationship, will be recorded. The severity of the effect will be noted as *Mild, Moderat*e, or *Severe* according the following definitions:

Mild Awareness of signs or symptom, but easily tolerated.

Moderate Discomfort to a degree as to cause interference with normal daily life activities and

/or requiring medication.

Severe Incapacity with inability to work or do usual daily life activities and requiring medical

attention/intervention.

Causal Relations of Adverse Event/Experience

When determining the causal/effect relationship to the test product, the relationship will be described as Not related, Unlikely related, Possibly related or Related.

The following definitions will be utilized:

Not related No association to the test product. Related to other etiologies such as

concomitant medications or conditions or subject's known clinical state.

Unlikely related Uncertain association. Other etiologies are also possible.

Possibly related Clear-cut association with improvement upon withdrawal of the test

product. Not reasonably explained by the subject's known clinical state.

Related An adverse event with a clear-cut temporal association with exposure to

study materials and cannot reasonably be explained by the subject's known clinical state. Association with study material is confirmed by laboratory

testing if possible.

Serious Adverse Event/Experience

A Serious Adverse Event/Experience is any adverse experience occurring at any dose that results in any of the following outcomes:

- Death;
- A life-threatening adverse drug experience;
- Inpatient hospitalization or prolongation of existing hospitalization;
- A persistent or significant disability/incapacity;
- Congenital anomaly/birth defect;
- An important medical event that may require medical or surgical intervention to prevent one of the previously listed outcomes.

Unexpected Adverse Event/Experience

An Unexpected Adverse Event/Experience is any adverse drug event/experience not listed in the current labeling for the test product or the current IB. Where test product labeling or IB is not available, anticipated experiences will be based on the known pharmacological/toxicological properties of the test product or ingredients.

Follow-up:

If an adverse event/experience occurs, the subject under the direction of the PI or designated sub-investigator trained by the PI may be referred to the nearest acute care facility for treatment. Serious or Unexpected Drug Event/Experience will be followed to resolution. Any adverse event will be documented on an Adverse Event Report Form.

Recording and Reporting

The PI or designee records all adverse events on an Adverse Event Form in the subject's CRF.

The PI must promptly report all treatment related adverse events to the PDI study monitor.

All SAE must be reported to the:

- Sponsor within 24 hours of the PI awareness/notification of the event.
- IRB/IEC within 10 working days of the PI awareness/notification of the event.

If a subject has no adverse event during the study, the absence of such must be recorded on the CRF.

9 Statistics

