In this study four products will be tested and each subject will receive two products in the same time, one on the left side and the other on the right side. More than 100 randomization schemes will be generated to compensate for the baseline requirement failure and to provide enogh evaluable sites. The block randomization method will be used to ensure equal sample size groups over time. Products will be randomized in blocks of 12 and sampling time points will be randomized in blocks of 6. Randomization scheme will be generated using an electronic online randomizer provided by Urbaniak et al. (2013).

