3.7 Study Duration

The expected duration of this study for each subject is up to 3 weeks. Subjects will undergo at least a 14-day washout period before Treatment Day. The treatment day will be scheduled no sooner than 14 days from the washout visit. Each subject who chooses to participate in this study will be required to stay in the test facility for one scheduled Treatment Day.

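### The causality scale in section 8.3 is out of order: an adverse event with a plausible but uncertain product link fits only Unlikely related

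*Combined protocol and SAP*

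**What the plan says.** Section 8.3 (Adverse Events) defines four causality grades. Leaving aside Not related, they read as follows.

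- *Unlikely related*: "Uncertain association. Other etiologies are also possible".
- *Possibly related*: "Clear-cut association with improvement upon withdrawal of the test" product, followed by "Not reasonably explained by the" subject's clinical state as known.
- *Related*: "An adverse event with a clear-cut temporal association with exposure to" study materials, which clinical state cannot reasonably explain. It adds "Association with study material is confirmed by laboratory" testing, but only if that is possible.

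Under Recording and Reporting, the same section says "The PI must promptly report all treatment related adverse events to the PDI study monitor". It does not say which of the four grades count as treatment related. Serious events go to the sponsor within 24 hours, with no causality condition. Section 8.1 asks for the causal relationship to be described for every adverse event.

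On exposure, section 3.7 has each subject "stay in the test facility for one scheduled Treatment Day", and section 3.4 says that "each subject will receive two products in the same time, one on the left side and the other on the right side". Table 2 in section 5.1.2.2 gives an application time of 120 seconds for all four products.

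**The concern.** A causality scale should ask for more evidence at each step up, and a middle grade usually exists to hold events for which a product role is plausible but not established. Here the middle grade demands a clear-cut association and adds a withdrawal condition that the top grade lacks. Uncertainty is mentioned only in the grade labelled unlikely.

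An investigator who follows the definitions literally would place a plausible but uncertain local reaction on the unlikely side. Section 8.1 names skin irritation scores and adverse events as the principal safety measures. At stake are the causality grade recorded for such an event and, because prompt notification of the monitor is tied to treatment-related events, how soon the sponsor hears of a non-serious one.

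**Working it through.** No arithmetic is needed to settle the point, and the plan gives no figure to reproduce. The check sets the definitions in 8.3 side by side and traces types of event through them.

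**Step 1: criteria by grade.**

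| Criterion | Unlikely related | Possibly related | Related |
|---|---|---|---|
| Association | uncertain | clear-cut | clear-cut, temporal |
| Improvement on withdrawal | not mentioned | required | not required |
| Clinical state excluded as explanation | no; other causes possible | required | required |
| Laboratory confirmation | not mentioned | not mentioned | only if possible |

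Possibly related has three unconditional criteria. Related has two, plus one conditional criterion. Where laboratory confirmation is not possible, Possibly related is the harder grade to meet.

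**Step 2: does withdrawal fit the design?** Each test area is treated once, for 120 seconds, on one day, so there is no continuing treatment to stop. The nearest equivalent is in section 5.1.2.3: residue is washed off as necessary after the final sample. The last scheduled skin scoring comes before that sample. Taking nominal times from the start of application (Table 2 and section 5.1.2.3), the final sample falls at:

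- products A, B and C: 120 + 180 (minimum drying) + 600 = 900 seconds, or 15 minutes;
- product D: 120 + 90 + 600 = 810 seconds, or 13.5 minutes.

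No skin scoring is scheduled after the wash-off (sections 5.1.2.3 and 17.1). Section 8.1 ends adverse event capture at discharge, and 8.3 requires follow-up to resolution only for serious or unexpected events. For an expected, non-serious local reaction, improvement may therefore often go unobserved.

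**Step 3: trace the events.**

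- *Clear-cut temporal link, not explained by clinical state.* This meets Related without any evidence of improvement. It is not downgraded.
- *Plausible link, but another cause is also possible.* Such causes are built into the procedures. Clipping may take place about 48 to 96 hours before treatment (5.1.1), and folliculitis from clipping is a listed risk (7.1). Each sampling site is scrubbed twice for one minute (5.2.1). By the 10-minute skin assessment, two of the three sites in each area, baseline and 30 seconds, have been scrubbed in this way. Clipping and scrubbing are not obviously part of the subject's clinical state, so the exclusion clause may not be what fails. What fails is the requirement that the association be clear-cut. Neither upper grade is met, and the wording of Unlikely related describes the event exactly.
- *Serious event, any grade.* It is reported within 24 hours.

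**Step 4: follow the grade downstream.** Under 8.1 it is described for every event. Under 8.3 it bears on prompt notification, through a term that is not mapped to the grades. It does not enter the planned tables: sections 8.2 and 9.4 summarise incidence by treatment group, with listings, and no restriction by causality.

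**The case against.** The strongest defence is that little depends on the grade. All adverse events are recorded whatever their causality, entered in the case report form and open to the sponsor's monitor. A post-treatment irritation score of 3 is an adverse event automatically (17.6). Serious events follow their own reporting rule. This stands, and it confines the consequence to the recorded grade and to the timing of notice for non-serious events. It does not repair the scale, because recording an event is separate from judging its cause and from notifying it promptly.

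A reader might also infer more than the documents support.

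- *That Possibly related is stricter than Related in every respect.* It is not. Related specifies a temporal association and adds laboratory confirmation where possible.
- *That plausible product reactions in general are graded Unlikely related.* They are not. A new reaction at a treated site, with clear timing and no explanation by clinical state, is Related.
- *That improvement on withdrawal can never be seen.* This is too absolute. Residue may be washed off, duration and outcome are described for every event (8.1), and 8.3 refers to a follow-up period.
- *That prompt reports will be missed.* This is an inference. Nothing in 8.3 states that Unlikely related falls outside treatment related, although that is the ordinary reading.
- *That product-related event rates will be understated in the report.* No such rate is planned. The sentence in 8.1 on categorising events by product can be read as assigning the event to the product used on that side.

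**Conclusion.** The concern holds in a limited form. The definitions in 8.3 are not graded, the withdrawal condition suits a single brief application poorly, and an event with a plausible but uncertain product link can be placed only in Unlikely related. The wording should be corrected, since the rule as written produces a wrong grade for a foreseeable kind of event.

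The effect is confined to the causality grade of uncertain events and to prompt notification of the non-serious ones among them. Efficacy analyses, planned adverse event tables and serious event reporting are untouched. The documents give no adverse event counts, so the number of events affected cannot be stated.

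The conclusion assumes that investigators apply the definitions as written. The part on notification also assumes that treatment related is read as excluding Unlikely related; on any other reading, the term is still undefined.

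**What to change.** In section 8.3, reconcile the definitions so that each grade asks for more than the one below it. One wording that does this:

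- *Possibly related*: reasonable temporal association with exposure; a role of the product cannot be excluded, although other causes are possible. Remove the withdrawal condition.
- *Unlikely related*: the temporal association is improbable, or another cause is more likely.
- *Related*: may stay as it is.

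Under Recording and Reporting, add that treatment related means Possibly related or Related.

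The change is two reworded definitions and one added sentence, with no effect on design, sample size or analysis. The downside is that slightly more non-serious events will be graded and reported as related.

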9.1 Data sets analyzed

A modified intent to treat data set will be used for efficacy analysis. Subjects with treatment day baseline bacterial count in the range of 5.00 to 7.50 log₁₀/cm², inclusive, on the groin will be included

in the modified intent to treat data set. The acceptability of each bilateral baseline site (left or right) will be assessed separately for inclusion in the modified intent to treat data set. The exclusion of subjects who do not meet treatment day baseline requirements and the exclusion of either left or right groin sites without exclusion of the subject as a whole makes this data set a modified intent to treat data set.

A per protocol data set will also be used for efficacy analysis. Subjects included in the modified intent to treat data set with no major protocol deviations and no missing for one or more of the 30 minutes and 10 minutes time points will be included in the per protocol data set. The acceptability of each bilateral site (left or right) will be assessed separately for inclusion in the per protocol data set.

The full intent to treat data set (all randomized subjects) will be used for safety analysis.

9.2 Sample Size

This evaluation will be performed with an estimated of a minimum of 50 evaluable sites per product with qualifying treatment day microbial baseline counts. No sample size calculation was performed to provide statistically-powered evidence of efficacy as part of this study.

9.3 Efficacy Analyses

An alpha level of 5% will be used for all analyses.

The following descriptive statistics for log_{10} CFU/cm² and for log_{10} CFU/cm² reductions from Baseline will be computed for each treatment, grouped by body area and each post application sampling time point (30 seconds, 10 minutes and/or Baseline, by case): mean, median, standard deviation, minimum, maximum, and count.

The statistician will be blinded to the treatment during the analysis phase.

9.3.1 Efficacy Analysis

A linear regression model for each post treatment sampling time point of immediate efficacy (30 seconds and 10 minutes post-application) will be used. In the model, the dependent variable used will be the post treatment bacterial count (\log_{10} CFU/cm²) and predictors will be the treatment as a fixed effect and the Baseline as a covariate. The ATE corrected for Baseline will be estimated from the model and compared to non-inferiority criteria.

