3.1 Overall Study Design and Plan

This study is designed to determine the antimicrobial effectiveness of three treatments (A, B and C), intended for use as Patient Preoperative Skin Preparation. The testing methods are based on the standardized test method ASTM E1173-15, Evaluation of Preoperative, Precatheterization, or Preinjection Skin Preparations, and using the requirements specified by in the 2017 FDA 21 CFR Part 310, Safety and Effectiveness of Health Care Antiseptics; Topical Antimicrobial Drug Products for Over-the-Counter Human Use, Final Rule (December 20, 2017). The immediate antimicrobial efficacy will be evaluated in this study.

At least 100 subjects will be treated bilaterally with two of the four test materials (A, B, C and Positive Control), one per each side of the groin test site. Subjects will undergo at least a 14-day washout period before Treatment Day. During Treatment Day subjects who meet the Inclusion Criteria will be treated with the study products and samples will be taken before and after treatment application. The cup scrub technique will be used for sampling baseline, 30-seconds and 10-minutes on the Treatment Day.

The immediate antimicrobial efficacy at 30 seconds and 10 minutes post-application will be demonstrated if the non-inferiority of the ATE of the investigational products (A, B and C) compared to Positive Control (D) is met (the upper two-sided 95% confidence bound of the post-application microbial counts corrected for Baseline of the investigational products A, B or C compared to the Positive Control should be less than 0.5 log₁₀).

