3.11 Protocol Modifications

3.11.1 Protocol Amendments

Protocol Amendments will not be implemented without prior agreement between the PI and PDI and prior submission and approval from the IRB/EC, except when necessary to eliminate an immediate hazard to the subject and to protect the safety and well-being of the subject.

Will constitute Protocol Amendments for administrative inputs and changes: correction of typing mistakes, changes in study personnel (other than the PI) or contact information. Protocol Amendments for administrative inputs and changes has to be agreed between the PI and PDI and will be submitted to the IRB/EC but implementation may proceed without prior IRB/EC approval, unless so required by the IRB/EC or site SOPs.

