5.1.2.1.1 Preparation of Groin Test Area

The test site within the groin region (groin test area) is defined as the inner aspect of the uppermost thigh, one inch parallel distance to the inguinal crease and where skin to skin contact is expected. Where subjects present with deep inguinal folds at the crease, the sampling distance from the crease may be increased to avoid skin folds in the sampling area. The corners of each groin test area will be marked directly on the skin using a non-toxic skin marker. Three sampling sites will be numbered within each groin test area, on each side of the groin region. The positioning and numbering of the groin sampling sites are standard for all subjects. Sampling sites on the contra-lateral side of the groin will be numbered in a mirror-image orientation. The three sampling sites within each test area represent one baseline (pre-prep) site and two post-prep sample sites (30 seconds and 10 minutes).

Test sites for the investigational product and active control applicator on the groin will be $1.5'' \times 5''$ (3.81 cm x 12.7 cm) in area, occur at the uppermost inner aspects of both thighs, and appear to be similar in condition.

After groin test areas are marked and sample sites numbered, baseline samples will be collected from the appropriate site per the randomization schedule in each test area using the scrub cup technique (section 5.2.1).

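### The efficacy regression ignores that each subject supplies two groin sites with different products; with positive within-subject correlation its intervals are too wide and the precision of the paired design is lost

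*Combined protocol and SAP*

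**What the plan says.** - **Design.** Under section 3.1, subjects are "treated bilaterally with two of the four test materials". Section 3.4 says that "each subject will receive two products in the same time, one on the left side and the other on the right side", and that "Products will be randomized in blocks of 12". The schedule itself is in a separate document.
- **Unit of analysis.** Section 9.1: "The acceptability of each bilateral baseline site (left or right) will be assessed separately for inclusion" in the modified intent-to-treat set. The per-protocol set is also built site by site. The unit is therefore the site.
- **Model.** Section 9.3.1 and the synopsis (Statistical Methods) specify a separate linear regression at 30 seconds and at 10 minutes, in which "predictors will be the treatment as a fixed effect and the Baseline as a covariate". No other term or error structure appears anywhere in the document.
- **Criterion.** Section 2.1 compares the upper limit of the two-sided 95% interval for A-D, B-D or C-D with 0.5 log10.
- **Size.** Section 9.2 sets a minimum of 50 evaluable sites per product and states that no power-based calculation was made.

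**The concern.** Ordinary regression treats all sites as independent. A subject's two sites share the person, the washout and the Treatment Day, and section 5.1.2.1.1 asks that they "occur at the uppermost inner aspects of both thighs, and appear to be similar in condition". Adjusting for each site's own baseline may absorb part of what they share, but there is no reason to expect it to absorb all of it. Some positive residual correlation is therefore plausible.

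The two sites of a subject always carry different products. Positive correlation then makes the true variance of a between-product difference smaller than the model reports. Two losses follow:

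1. The reported standard error is too large for the estimator being used.
2. The estimator does not weight the within-subject comparisons that the bilateral design provides.

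Each success claim rests on one confidence limit, and nothing in the plan shows that there is precision to spare. What is at risk is that a product that is truly non-inferior fails.

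**Working it through.** **Inputs from the plan.** At least 100 subjects, two sites each, four products, margin 0.5 log10, two-sided 95% interval. The only planned figure that can be reproduced is the site count: 100 × 2 / 4 = 50 per product, which agrees with section 9.2.

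**Assumptions not in the plan.** The residual within-subject correlation rho; the residual SD s; and equal use of all six product pairs. The last fits blocks of 12 (six pairs × two side orders) but is not stated. Two cases are shown:

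- *Full pairing*: 100 complete pairs, so 100/6 = 16.67 subjects per product pair.
- *60% pairing*: 60 complete pairs (10 per product pair) plus 20 single sites per product, because section 9.1 drops sites singly.

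**Step 1: what ordinary regression reports.** Var(A-D) = 2s²/50 = 0.04s².

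**Step 2: the true variance of that same estimate.** With m subjects carrying both A and D, Var = 0.04s² − 2m·rho·s²/2500.

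- Full pairing: 0.04s²(1 − rho/3).
- 60% pairing: 0.04s²(1 − rho/5).

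Reported SE / true SE under full pairing is 1/√(1 − rho/3). The actual one-sided error at the margin is 1 − Φ(1.96/√(1 − rho/3)), against a nominal 2.5%.

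**Step 3: variance when the correlation is modelled** (generalised least squares, rho known).

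- Full pairing: 0.04s²(1 − rho²)/(1 + rho/3).
- 60% pairing: 0.04s² × 50(1 − rho²)/(50 + 10rho − 20rho²).

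Example, full pairing at rho 0.5: 0.75/1.1667 = 0.643 and √0.643 = 0.802, so the interval is 20% narrower.

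**Step 4: power** for one product at one time point, true difference 0, s = 1.2. With independent sites SE = 0.2 × 1.2 = 0.24 and power = Φ(0.5/0.24 − 1.96) = Φ(0.123) = 55%. The planned analysis stays near 55% across the rho range below. With the correlation modelled, power = Φ(0.5/SE − 1.96).

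| rho | Reported/true SE, full | One-sided error, full | Narrowing, full | Narrowing, 60% | Power, full | Power, 60% |
|---|---|---|---|---|---|---|
| 0 | 1.000 | 2.5% | 0% | 0% | 55% | 55% |
| 0.1 | 1.017 | 2.3% | 2% | 1% | 57% | 56% |
| 0.2 | 1.035 | 2.1% | 5% | 3% | 59% | 58% |
| 0.3 | 1.054 | 1.9% | 9% | 6% | 63% | 60% |
| 0.5 | 1.095 | 1.6% | 20% | 13% | 74% | 67% |
| 0.7 | 1.142 | 1.3% | 36% | 27% | 90% | 81% |

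The second and third columns measure the error in the planned interval. The narrowing columns measure the total gain from changing the model.

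**Step 5: sensitivity.**

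- *SD*, at rho 0.3 with full pairing, planned versus modelled: s = 0.8, 89% versus 93%; s = 1.0, 72% versus 78%; s = 1.5, 38% versus 45%. For s = 1.0 the modelled SE is 0.2 × √0.827 = 0.182.
- *Negative correlation*, rho = −0.2: √(1 + 0.2/3) = 1.033, so the planned interval is about 3% too narrow and the one-sided error is 2.9%.
- *Pairing pattern*, rho 0.5: reported/true SE is 1.41 for a product always paired with D and 1.00 for one never paired with D.

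**Step 6: simulation.** With a baseline covariate (8,000 runs per setting, 51 sites per product), the planned regression gave a reported/true SE ratio of 1.01, 1.05, 1.09 and 1.16 at rho 0, 0.3, 0.5 and 0.7, with one-sided error 2.5%, 2.1%, 1.6% and 1.1%. In a second simulation (2,000 trials per cell, s = 1.2), a REML compound-symmetry model gave power of 53/56/60/61/74/88% (full) and 54/56/57/59/67/80% (60%) at rho 0/0.1/0.2/0.3/0.5/0.7. Its false non-inferiority rate was 2.2% to 3.2%, with a Monte Carlo standard error of about 0.35 percentage points.

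**The case against.** The strongest reply is that the planned analysis is simple, prespecified and, for positive rho, errs on the safe side. The reported interval is only modestly too wide (about 4% to 14% for rho 0.2 to 0.7 under full pairing); the rest of the gain comes from a more efficient estimator. No power target is stated, so none is missed. The 50 sites are a minimum and sections 3.4 and 3.8.2 allow more subjects. Finally, rho, SD and the pairing pattern are all undocumented, baseline may absorb much of the shared variation, and the similar appearance of two sites says little about correlation of post-treatment counts.

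Most of this stands as a limit on size. The two effects should be read separately, and at small rho the gain is small. Simulated power at rho 0.3 and 0.7 is one to two points below the formula, which treats rho as known. The simulation used a fixed 120 degrees of freedom in place of the Kenward-Roger method proposed below, so the exact method has not been tested.

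It does not remove the point. The standard error is wrong whenever rho is not zero and the compared products share subjects. Conservatism protects against false claims, not against failing the study's stated objective. For positive rho, no pairing pattern examined made the planned interval too narrow, so the direction does not depend on the unlisted schedule.

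**Conclusion.** The concern holds and should be fixed. The omission is certain from the text. The direction is conservative if rho is positive, which is plausible but not documented. The size depends on rho, SD and the pairing: at rho 0.3 the gain in interval width is 6% to 9% and at rho 0.5 it is 13% to 20%, the lower figure being for 60% pairing. Under full pairing, rho 0.5 corresponds to about 78 independent sites per product (50/0.643) instead of 50. Results under the current model would remain interpretable, with no inflation of false non-inferiority for positive rho and a slight one if rho is negative. What is lost is precision that the design already collects, in a trial with no calculation to show that 50 sites are enough.

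**What to change.** In section 9.3.1 and the synopsis, keep treatment and baseline and add the within-subject correlation. Suggested text:

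> At each time point a linear mixed model (REML) with treatment and Baseline as fixed effects and a compound-symmetry covariance for sites of the same subject will be fitted, with Kenward-Roger degrees of freedom. Subjects with one evaluable site are included. A-D, B-D and C-D and their two-sided 95% confidence intervals will be taken from this model.

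Compound symmetry also allows a negative correlation. A random subject intercept, or another stated small-sample degrees-of-freedom method, is acceptable. The protocol should also state which product pairs are used and whether equally often.

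**Cost.** One changed model statement and a line on pairing; no new subjects, samples or visits. The change is not administrative, so section 3.11.1 requires "prior submission and approval from the IRB/EC". The sponsor should confirm that the term is compatible with the regulatory criteria cited in sections 1 and 3.1, which cannot be checked from these documents.
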